7.2. Demographic analysis

Demographics and baseline characteristics will be summarized for all recruited patients following the standard tables detailed in Section 11 (Appendix II).

Continuous variables will be summarized and presented with summary statistics, i.e., median and range, mean, standard deviation and categorical variables will be summarized in frequency tables.

In case of pre-treatment characteristics with multiple measurements per patient before the start of treatment (laboratory assessments, vital signs) the baseline measurement will be considered the last value prior to or on the first day of treatment.

Age, sex, baseline weight, height, BSA, Eastern Cooperative Oncology Group performance status (ECOG-PS), vital signs (heart rate, blood pressure and body temperature), left ventricular ejection fraction (LVEF), electrocardiogram (ECG), signs and symptoms and concomitant medication results will be summarized descriptively. Age is calculated based on the date of birth at the time date of registration date.

Age will be calculated based on the date of birth and the date of informed consent and rounded to integer numbers (by defect).

$$Age = \frac{\text{(date of informed consent) - (date of birth)}}{365.25}$$

Tumor characteristics: histology diagnosis, primary site, time from diagnosis, stage, number of organs involved and sites of disease, time from last documentation of PD before start of treatment with Zalypsis® will be described.

A frequency tabulation of the number of patients with the different types of previous cancer surgery, radiotherapy and systemic anticancer therapy will be given.

A summary of prior relevant history and signs and symptoms will be presented per patient. Laboratory values at baseline will be tabulated. Median values, ranges and NCI-CTCAE grades will be displayed by laboratory parameters.

7.3. Statistical methodology for efficacy

The main efficacy analysis will be performed in the efficacy population. A sensitivity analysis of efficacy results will be done in the population of all treated patients (safety population).

Binomial estimates with exact 95% confidence intervals (CIs) will be calculated for the analysis of the main endpoint (ORR). Time-to-event endpoints (DOR, PFS3, PFS6 rates and OS rate at 12 months) will be analyzed according to the Kaplan-Meier method.

If relevant, efficacy parameters versus baseline covariates will be analyzed and appropriate test will be used (i.e., the Fisher exact test for categorical variables, the log-rank test or Cox regression for time-to-event variables, etc.).

Graphical representations of tumor shrinkage will be represented by waterfall plots or spider plots if applicable.

Statistical tests, if and when they are carried out, will only have an exploratory purpose and have a threshold of $\alpha = 5\%$.

See Section 11 (Appendix II) for further details on the efficacy analysis and Section 13 (Appendix IV) for graphic templates.

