3. OVERALL STUDY DESIGN

This is a multicenter, open-label, single-arm, non-comparative, phase II clinical trial with single-agent Zalyps[®] given as a 1-h i.v. infusion on d1, d8 and d15, q4wk, to patients with advanced and/or metastatic EFT who failed to standard chemotherapy.

The primary endpoint of the study is the overall response rate (ORR), defined as the percentage of patients with objective response (OR), either complete response (CR) or partial response (PR), as defined by the Response Evaluation Criteria in Solid Tumors (RECIST) v1.1.

The study will consist of two stages. If in the first stage there are no responders after testing the drug on 12 evaluable patients, the trial will be terminated. If there are ≥ 1 responders the trial will go on to the second stage and 17 additional evaluable patients will be accrued. A total of 29 evaluable patients will be studied. If the total number of responders is ≤ 2 , the drug will be considered as not interesting in the setting of patients treated for this disease with this schedule.

Treatment will be administered in the absence of disease progression and/or unacceptable toxicity. In case of obtaining a CR, two additional cycles will be administered and then the treatment will be stopped.

A disease evaluation will be performed at baseline and every other cycle (± 1 week) until evidence of disease progression.

Patients will be evaluated using clinical and laboratory assessments before and after each treatment cycle. Any treatment-related AEs will be followed-up until the events or their sequelae resolve or stabilize at a level acceptable to the Investigator and the Sponsor(s). Patients no longer receiving study treatment will be followed up for survival (see Section [5.2](#)).

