10.1. SAMPLE SIZE

The optimum two-stage design to test the null hypothesis that the overall response rate (ORR) is $\leq 3\%$ versus the alternative that $ORR \geq 20\%$ was selected. After testing the drug on 12 patients in the first stage, the trial will be terminated if there is not any responder. If the trial goes on to the second stage, a total of 29 patients will be studied, 12 from the first stage and 17 from the second stage. If the total number responding is less than or equal to 2 (two patients), the drug will be considered not interesting in the setting of patients treated with this disease and with this schedule. This design has an expected sample size of 17.20 and a probability of early termination of 0.69. If the drug is actually not effective, there is a 0.05 probability of concluding that it is (type I error). If the drug is actually effective, there is a 0.1 probability of concluding that it is not (type II error).

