2.4.4 Special Notes on Response Assessment

When nodal disease is included in the sum of target lesions and the nodes decrease to 'normal' size (< 10 mm), they may still have a measurement reported on scans. This measurement should be recorded even though the nodes are normal in order not to overstate progression should it be based on increase in size of the nodes. As noted earlier, this means that patients with CR may not have a total sum of 'zero' on the CRF.

In trials where confirmation of response is required, repeated 'NE' time point assessments may complicate best response determination. The analysis plan for the trial must address how missing data/assessments will be addressed in determination of response and progression. For example, in most trials it is reasonable to consider a patient with time point responses of PR-NE-PR as a confirmed response

Patients with a global deterioration of health status requiring discontinuation of treatment without objective evidence of disease progression at that time should be reported as 'symptomatic deterioration'. Every effort should be made to document objective progression even after discontinuation of treatment. Symptomatic deterioration is not a descriptor of an objective response: it is a reason for stopping study therapy. The objective response status of such patients is to be determined by evaluation of target and non-target disease as shown in **Tables 1–3**.

Conditions that define 'early progression, early death and inevaluability' are study specific and should be clearly described in each protocol (depending on treatment duration, treatment periodicity).

In some circumstances it may be difficult to distinguish residual disease from normal tissue. When the evaluation of complete response depends upon this determination, it is recommended that the residual lesion be investigated (fine needle aspirate/biopsy) before assigning a status of complete response. FDG-PET may be used to upgrade a response to a CR in a manner similar to a biopsy in cases where a residual radiographic abnormality is thought to represent fibrosis or scarring. The use of FDG-PET in this circumstance should be prospectively described in the protocol and supported by disease specific medical literature for the indication. However, it must be acknowledged that both approaches may lead to false positive CR due to limitations of FDG-PET and biopsy resolution/sensitivity.

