2.9 Reporting Best Response Results

2.9.1 Phase II Trials

When response is the primary endpoint, and thus all patients must have measurable disease to enter the trial, all patients included in the study must be accounted for in the report of the results, even if there are major protocol treatment deviations or if they are not evaluable. Each patient will be assigned one of the following categories:

1. Complete response.
2. Partial response.
3. Stable disease.
4. Progression.
5. Inevaluable for response: specify reasons [for example: early death, malignant disease; early death, toxicity; tumor assessments not repeated/incomplete; other (specify)].

Normally, all eligible patients should be included in the denominator for the calculation of the response rate for phase II trials (in some protocols it will be appropriate to include all treated patients). It is generally preferred that 95% two-sided confidence limits are given for the calculated response rate. Trial conclusions should be based on the response rate for all eligible (or all treated) patients and should not be based on a selected 'evaluable' subset.

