4.1.1. Efficacy population

To be evaluable for efficacy, eligible patients must have received at least four infusions of the six infusions corresponding to the first two cycles and have at least one disease measurement recorded not less than six weeks after treatment onset.

In addition, any eligible patient who receives at least two of the three infusions in one treatment cycle and develops disease progression or dies due to progressive disease (PD) prior to response evaluation will be considered evaluable for the main endpoint (ORR) and will be categorized as an "early progression".

Patients withdrawn due to toxicity without any tumor assessment after the start of study treatment will be considered as "treatment failures" and will not be replaced.

Patients withdrawn due to significant clinical deterioration of unknown reason, or due to hypersensitivity reactions or unrelated AEs, and patients who refuse to continue on study for any reason without any tumor assessment after the start of study treatment will be considered not evaluable for efficacy and will be replaced.

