6.1. Sample size determination

In this phase II trial, an optimum two-stage design to test the null hypothesis that the ORR is \leq 3% versus the alternative that ORR \geq 20% was selected. After testing the drug on 12 patients in the first stage, the trial will be terminated if there is not any responder. If the trial goes on to the second stage, a total of 29 patients will be studied, 12 from the first stage and 17 from the second stage. If the total number responding is less than or equal to 2 (two patients), the drug will be considered not interesting in the setting of patients treated with this disease and with this schedule.

This design has an expected sample size of 17.20 and a probability of early termination of 0.69 under the null hypothesis. If the drug is actually not effective, there is a 0.05 probability of concluding that it is (type I error). If the drug is actually effective, there is a 0.1 probability of concluding that it is not (type II error).

7. Statistical analysis

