8.6. Interim Analysis

A futility analysis is planned when 12 patients evaluable for efficacy are recruited according to the Simon's design. Other non-scheduled analyses might be performed exclusively for enhancing patient's safety.

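### The go/no-go decisions and the primary ORR use an evaluable set, defined by events after treatment starts, that leaves out known or near-certain non-responders, so activity in treated patients can be overstated

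*SAP*

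**What the plan says.** **Which set is used.** SAP section 7.3: "The main efficacy analysis will be performed in the efficacy population". It adds a sensitivity analysis in all treated patients. SAP section 8.6: "A futility analysis is planned when 12 patients evaluable for efficacy are recruited". Protocol section 3: "If in the first stage there are no responders after testing the drug on 12 evaluable patients, the trial will be terminated"; the total of 29 there is also labelled evaluable. The sample-size sections drop the label. SAP section 6.1 has "After testing the drug on 12 patients in the first stage, the trial will be terminated if there is not any responder", and Protocol section 10.1 has "a total of 29 patients will be studied, 12 from the first stage and 17 from the second stage".

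**Who is evaluable (SAP section 4.1.1; Protocol sections 8.1 and 10.3.1).**
- At least four of the first six infusions, and a disease measurement at six weeks or later.
- As an early progression: "any eligible patient who receives at least two of the three infusions in one treatment cycle and develops disease progression or dies" of it before response evaluation.
- Toxicity withdrawals with no scan on treatment count as treatment failures and are not replaced.
- Withdrawals with no scan for unexplained deterioration, hypersensitivity, unrelated AEs or refusal are not evaluable and are replaced (also Protocol section 5.3).

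**What the protocol's RECIST summary says.** Appendix 3, section 2.9.1: "Trial conclusions should be based on the response rate for all eligible (or all treated) patients and should not be based on a selected" subset of evaluable patients. Appendix 3, section 2.4.4, says that the conditions for early progression, early death and inevaluability "are study specific and should be clearly described in each protocol".

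**The concern.** Every element of the evaluability rule is observed after the first infusion, so membership can depend on how the patient fares. The plan limits this by counting early progression and unscanned toxicity stops against the drug, but three groups of treated patients still fall outside the denominator:

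1. Unscanned withdrawals for the four listed reasons. With no post-baseline assessment, none can have a confirmed response.
2. Progression, or death from it, after a single infusion. These are known non-responders, but the early-progression rule needs two infusions in one cycle.
3. Withdrawals for toxicity, refusal or an unrelated AE with fewer than four infusions, whose end-of-treatment scan shows no progression. They miss the infusion minimum, did not progress and are not unscanned, so no rule takes them in.

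For toxicity stops, group 3 has a perverse result. Protocol section 5.8 requires a tumor assessment at end of treatment whatever the reason for stopping. An unscanned patient counts as a failure; the same patient, scanned as required and found stable, is excluded.

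Groups 2 and 3 are not on the replacement list, but accruing until 12 and then 29 patients are evaluable has the same effect. At stake are the decision to continue, the judgement on whether the drug is of interest, and the headline ORR.

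**Working it through.** **Inputs.** Null ORR 3%, alternative 20%; stop at 0 responders in 12; three or more responders in 29 needed (SAP section 6.1). The documents give no non-evaluable rate, so f, the share of treated patients excluded, is assumed and shown over a range.

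**1. Reproduce the design.** With b(x; n, p) the binomial probability:
- Early stop: PET = (1 − p)^12. At 3%, 0.97^12 = 0.694 (stated 0.69).
- Expected size: 12 + (1 − 0.6938) × 17 = 17.20 (stated 17.20).
- P(declare active) = Σ over x = 1 to 12 of b(x; 12, p) × P[Bin(17, p) ≥ max(0, 3 − x)]. At 3% this is 0.0460 (stated 0.05); at 20% it is 0.9005 (stated type II error 0.1).

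The design reproduces, with an exact type I error of 4.60%.

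**2. A group 3 case.** A patient stops for toxicity after all three Cycle 1 infusions, the last on Day 15. The end-of-treatment visit is at 30 ± 2 days: Day 15 + 28 to Day 15 + 32, that is Day 43 to Day 47. The scan shows stable disease. The six-week condition is met but three infusions are too few, so the patient is not evaluable; a scan exists, so the patient is not a treatment failure either.

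**3. Effect on ORR.** If no excluded patient responds, evaluable ORR = treated ORR / (1 − f). With three responders:

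| Denominator | Excluded | ORR | Exact 95% CI |
|---|---|---|---|
| 29 evaluable | – | 10.3% | 2.2–27.4% |
| 32 treated | 3 (f = 9.4%) | 9.4% | 2.0–25.0% |
| 36 treated | 7 (f = 19.4%) | 8.3% | 1.8–22.5% |

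**4. Effect on type I error.** This depends on what the 3% describes.
- *Evaluable patients:* 4.60%, unchanged.
- *All treated patients, excluded patients all non-responders:* the evaluable null rate becomes 0.03/(1 − f). Type I error is then 5.2%, 5.9% or 7.8% at f = 5%, 10% or 20%. It reaches 5% at an evaluable rate of 3.105%, so f = 1 − 0.03/0.03105 ≈ 3.4%. In patients, with f = k/(29 + k), it is 4.99%, 5.40% or 5.83% for k = 1, 2 or 3 exclusions.
- *All treated patients, excluded patients responding at 1.5%:* the evaluable null rate is (0.03 − 0.015f)/(1 − f). Type I error is 4.9%, 5.2% or 6.1% at the same f, passing 5% at f ≈ 6.6%.

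**5. Moving the unchanged rule to treated patients.** If 3% and 20% are all-treated rates, 4.60% and 90.05% hold exactly. If they are evaluable rates, the treated rates are 0.03(1 − f) and 0.20(1 − f):

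| f | Type I error | Power | Stage 1 stop if active |
|---|---|---|---|
| 0 | 4.6% | 0.901 | 6.9% |
| 10% | 3.5% | 0.858 | 9.2% |
| 20% | 2.6% | 0.800 | 12.3% |

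**The case against.** The case for the plan is substantial. The set is prespecified, and its main terms agree between protocol and SAP. The worst omissions are already counted as failures. An all-treated sensitivity analysis, all-treated tables and listings of exclusions are planned. Appendix 3 summarizes an outside guideline, hedges its sentence on the usual denominator, and leaves inevaluability to each protocol. All of that stands. But the sentence on trial conclusions carries no hedge, freedom to define inevaluability does not cancel it, and the sensitivity analysis drives neither decision.

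It can also be said that the exclusion of groups 2 and 3 is inferred: Protocol section 5.3 equates non-evaluable with the four unscanned reasons, and nothing classifies the other two groups expressly. That is fair. It shows a gap between section 5.3 and SAP section 4.1.1, not a rule that takes these patients in.

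A reader might infer more than the documents support:
- *That type I error exceeds 5%.* The design counts are repeatedly labelled evaluable (Protocol synopsis and section 3, SAP section 8.6), which favours reading the 3% as an evaluable rate. Inflation needs both an all-treated null and enough exclusions.
- *That the all-treated ORR is also biased*, because the footnote to SAP Table 11.2.1.5 repeats the two-infusion condition. The footnote affects only whether such a patient is shown as PD or NE; the denominator is all treated patients.
- *That the bias runs only upward.* Under Protocol section 7.2.3, a patient kept on treatment for clinical benefit after missing Days 8 and 15 could respond with fewer than four infusions and be excluded.
- *That the decision rules should move to treated patients in any event.* Step 5 shows the power lost if the rates are evaluable rates.

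**Conclusion.** The point holds. Both decisions and the primary ORR use a set fixed by events after treatment starts, and the definition as written drops known or near-certain non-responders. The likely direction is upward: group 1 cannot contain a confirmed responder and group 2 progressed, while group 3 could occasionally contain one. The size is 1/(1 − f) if no excluded patient responds, about one to two percentage points in the three-responder example, well inside the width of the confidence intervals. It rests on an assumed f.

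The error-rate consequence is conditional. It is absent if the 3% is an evaluable rate, and appears only if the 3% is an all-treated rate and f exceeds about 3.4% (6.6% if excluded patients respond at half the null rate). The plan never says outright which population the 3% and 20% describe. The definition should be fixed; the design itself is calculated correctly.

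**What to change.** - In Protocol sections 8.1 and 10.3.1 and SAP section 4.1.1, count progression, or death from it, after any infusion as early progression.
- Count every toxicity withdrawal without a confirmed CR or PR as a treatment failure, scanned or not.
- Count other treated patients with fewer than four infusions and a post-baseline scan by their actual response: non-responders unless CR or PR is confirmed. Reconcile Protocol section 5.3 with SAP section 4.1.1 accordingly.
- State which population the 3% and 20% describe.
- Show the all-treated ORR with its exact CI beside the evaluable ORR in SAP Table 11.2.1.3 and at both decision points. Base the conclusion about activity on it, or explain any disagreement.
- Apply 0/12 and 2/29 to the first 12 and 29 eligible treated patients only if 3% and 20% are all-treated rates. If they are evaluable rates, keep the rule on the corrected evaluable set.

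The cost is protocol and SAP wording and an adapted table shell. The reported ORR may be slightly lower, and power falls slightly if the 20% made no allowance for the newly counted non-responders.

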5.2. Secondary endpoints

- Duration of response (DOR): is defined as the time between the date when the response criteria (PR or CR, whichever is reached first) are fulfilled and the first date when disease progression, recurrence or death is objectively documented (taking the smallest measurements documented since the treatment started as reference for PD). DOR censoring rules are the same as for progression-free survival (PFS) and are described below.
- Progression-free survival (PFS): is defined as the time from the date of the first study drug administration to the date of documented progressive disease (PD) by RECIST v1.1 or death (regardless of the cause of death). If the patient receives further antitumor therapy before PD and within the timeframe expected for first follow-up, PFS will be censored on the date of the last disease assessment prior to the administration of this antitumor therapy. If the patient is lost to follow-up for the assessment of progression, or has more than one

missing follow-up between the date of last tumor assessment and the date of progression, death or further antitumor therapy, the PFS will be censored at the date of last valid tumor assessment before the missing evaluations. PFS at three and PFS at six months (PFS3 and PFS6) are defined as the Kaplan Meier estimates of PFS at these time points.

- Overall survival (OS): is defined as the time from the first day of study treatment administration to the date of death (or the last date when the patient is known to be alive). Survival will be followed every three months until death, or until the date of study termination, whichever occurs first. OS at 12 months (OS12) is defined as the Kaplan-Meier estimates of OS at this time point.
- Safety profile: adverse events (AEs), serious adverse events (SAEs), laboratory evaluations, deaths and the reason for study discontinuations, dose delays, modifications or omissions will be analyzed. All AEs and SAEs will be classified according to the NCI-CTCAE, v4.0, and will be coded using the Medical Dictionary for Regulatory Activities (MedDRA).

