11.2.2. Time-to-event variables

Table 11.2.2.1 Duration of response.

Summary*

N=XX

Events X (XX.X%)

Censored X (XX.X%)

Median XX 95% CI (XX.X-X.X)

(*) Responder patients by RECIST v1.1, i.e, CR and PR.

Table 11.2.2.2 Progression-free survival (Kaplan-Meier estimates in all evaluable patients).

Summary

N=XX

Events X (XX.X%)

Censored X (XX.X%)

Median XX 95% CI (X.X-X.X)

PFS rate at 3 months XX.X% 95% CI (XX.X%-XX.X%)

PFS rate at 6 months XX.X% 95% CI (XX.X%-XX.X%)

Table 11.2.2.3 Overall survival. (Kaplan-Meier estimates in all evaluable patients).

Summary

N=XX

Events X (XX.X%)

Censored X (XX.X%)

Median X.X 95% CI (XX.X-X.X)

OS rate at 12 months XX.X% 95% CI (XX.X%-XX.X%)

Table 11.2.2.4 Progression-free survival (Kaplan-Meier estimates in all treated patients).

Summary

N=XX

Events X (XX.X%)

Censored X (XX.X%)

Median XX 95% CI (X.X-X.X)

PFS rate at 3 months XX.X% 95% CI (XX.X%-XX.X%)

PFS rate at 6 months XX.X% 95% CI (XX.X%-XX.X%)

Table 11.2.2.5 Overall survival. (Kaplan-Meier estimates in all treated patients).

Summary

N=XX

Events X (XX.X%)

Censored X (XX.X%)

Median X.X 95% CI (XX.X-X.X)

OS rate at 12 months XX.X% 95% CI (XX.X%-XX.X%)

Table 11.2.2.6 Follow-up period.

Parameter	Median	95% CI Lower bound	95% CI Upper bound
PFS			
OS			

12. Appendix III. Safety evaluation

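### The main PFS and OS curves run from the first dose but use a set that patients join mainly on later events; all treated patients should be the headline set

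*SAP*

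**What the plan says.** SAP section 7.3 sets one rule for efficacy: "The main efficacy analysis will be performed in the efficacy population". It adds that "A sensitivity analysis of efficacy results will be done in the population of all treated patients (safety population". Neither sentence separates response from time-to-event endpoints.

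SAP section 4.1.1 defines the efficacy population. The main route has two conditions, both settled after treatment starts: "To be evaluable for efficacy, eligible patients must have received at least four infusions of the six infusions corresponding to the first two cycles", and patients must "have at least one disease measurement recorded not less than six weeks after treatment onset". Two further groups are kept: patients with at least two of three infusions in a cycle who progress or die of PD before response evaluation, and patients withdrawn for toxicity without a scan. A third group is declared not evaluable and is replaced: "Patients withdrawn due to significant clinical deterioration of unknown reason, or due to hypersensitivity reactions or unrelated AEs", together with refusals, where no tumour assessment followed the start of treatment.

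SAP section 5.2 times PFS and OS from the first administration. A PFS event is "documented progressive disease (PD) by RECIST v1.1 or death (regardless of the cause of death". A patient lost to follow-up for progression, or with more than one missed assessment before the event, is censored at the last valid assessment.

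The shells in SAP section 11.2.2 give each survival endpoint twice. For OS the titles are "Table 11.2.2.3 Overall survival. (Kaplan-Meier estimates in all evaluable patients" and "Table 11.2.2.5 Overall survival. (Kaplan-Meier estimates in all treated patients". Tables 11.2.2.2 and 11.2.2.4 do the same for PFS.

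**The concern.** A curve that starts at the first dose should include everyone who received that dose. Here the main set is filtered by what happened afterwards. By the main route, no patient can die before the six-week measurement, because reaching it is a condition of entry. Some patients who fail before then, and meet neither of the two exceptions, disappear from the main curve although their deaths are events under section 5.2.

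A response-evaluability filter is not needed for survival. Protocol sections 5.2 and 5.9 follow all patients until death or study termination, apart from those who withdraw consent, and censoring deals with incomplete follow-up.

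At stake are the headline PFS3, PFS6 and OS12. They would describe patients who reached a six-week scan or failed in a qualifying way, while the secondary objective concerns time-to-event efficacy of the treatment. With a single arm there is no internal comparator subject to the same filter.

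**Working it through.** **1. The plan's own figures (SAP section 6.1).** Stop at 0 of 12; not interesting at 2 or fewer of 29; 3% against 20%. Early termination under the null is 0.97^12 = 0.6938. Expected size is 12 + (1 − 0.6938) × 17 = 17.20. Exact type I error is 0.0460 and power 0.9005. The stated 0.69, 17.20, 0.05 and 0.1 all reproduce. The design is sound, and its sizes of 29 and 12 evaluable patients are used below.

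**2. Who is in the main curves (SAP section 4.1.1).**

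| Treated patient | In the efficacy population? |
|---|---|
| At least 4 of 6 infusions and a measurement at 6 weeks or later | Yes |
| PD or PD death before response evaluation, at least 2 of 3 infusions in a cycle | Yes, as early progression |
| Toxicity withdrawal, no scan | Yes, as treatment failure |
| Withdrawn without a scan: unexplained deterioration, unrelated AE, hypersensitivity, refusal | No; replaced |
| PD or death after a single infusion, not through toxicity | No |

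Table 11.2.1.4 agrees with rows 2 and 3: it lists treatment failures among evaluable patients and counts early PD only after two infusions. The early-progression clause is worded for ORR alone. Because Tables 11.2.2.2 and 11.2.2.3 cover all evaluable patients, row 2 appears to enter the survival curves, but the SAP does not say so.

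**3. Share of each window covered by the six-week condition (main route).** 42/91.3 = 46% for PFS3; 42/182.6 = 23% for PFS6; 42/365.25 = 11.5% for OS12.

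**4. Size of the shift.** Let k be the number of treated patients outside the efficacy population, and S_E and S_R the landmark rates in evaluable and removed patients. With complete follow-up to the landmark:

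- S_all = (29·S_E + k·S_R)/(29 + k)
- S_E − S_all = k/(29 + k) × (S_E − S_R)

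Neither k nor any expected landmark rate is in the documents, so these are assumptions:

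| k | 29/(29+k) | S_E = 30%, S_R = 0 | S_E = 30%, S_R = 15% | S_E = 50%, S_R = 0 |
|---|---|---|---|---|
| 1 | 0.967 | 29.0% | 29.5% | 48.3% |
| 3 | 0.906 | 27.2% | 28.6% | 45.3% |
| 6 | 0.829 | 24.9% | 27.4% | 41.4% |

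If S_R = S_E, the shift is zero for every k. If the trial stops at stage 1, the worst-case factor is 12/(12 + k): 0.923, 0.80 and 0.667 for k = 1, 3 and 6, which turns 30% into 27.7%, 24.0% and 20.0%.

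**5. PFS needs its censoring rule.** An unscanned patient's last valid assessment is the baseline one. If that patient is lost to follow-up, PFS is censored at baseline and the all-treated curve gains no event. Only early deaths and documented early PD move it. A simulation applied this rule: 29 evaluable patients with exponential PFS (median 2 months) plus a further exponential time to death (median 7 months), and about 4 removed patients. A removed patient's death before 16 weeks counted as a PFS event; otherwise PFS was censored at the start.

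| Median survival of removed patients | PFS3, evaluable v all treated | PFS6 | OS12 |
|---|---|---|---|
| 1 month | 35.5% v 32.1% | 12.6% v 11.2% | 42.0% v 37.0% |
| 9 months | 35.2% v 34.6% | 12.5% v 12.1% | 41.8% v 41.6% |

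All medians are assumptions. With short survival in the removed group the gap is largest for OS12, at 5.0 points. With survival close to that of evaluable patients it almost vanishes.

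**The case against.** The strongest reply is that the plan already reports the unconditioned estimates. Tables 11.2.2.4 and 11.2.2.5 carry the same medians, landmark rates and confidence intervals in all treated patients. Figures are planned for both sets where applicable, and excluded patients are listed with reasons. This stands: nothing is hidden, and what remains is which estimate leads.

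It can also be said that the SAP never ranks the two sets for PFS and OS by name, and that section 7.1 describes the efficacy population in terms of the main endpoint. That is fair as far as it goes. But section 7.3 speaks of efficacy generally and gives all treated patients only a sensitivity role, so its natural reading includes survival.

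A reader might infer that everyone who dies or deteriorates early without a scan is removed. The documents do not support that: PD death after two of three infusions in a cycle, and toxicity withdrawals, stay in. Nor do they show that removed patients are mostly early failures. Refusals and hypersensitivity withdrawals need not have a poor prognosis, and no outcomes are given for any removed group.

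The shift is also modest beside the sampling error. With 9 patients alive at 12 months, 9/29 = 31.0% and 9/32 = 28.1% differ by 2.9 points, while the approximate 95% half-width at n = 29 is 1.96 × √(0.31 × 0.69/29), about 17 points. These are secondary, descriptive endpoints, and the plan gives no historical benchmark or threshold for them. That limits the severity. It is not a reason to keep a filtered set as the headline when the unfiltered one is already planned.

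**Conclusion.** The point holds as a wrong choice of headline set for PFS and OS. Both clocks start at the first dose, while membership of the main set is decided mainly by later events.

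The expected direction is upward, on the condition that removed patients do worse than evaluable ones. In the worst case with 29 evaluable patients, a 30% rate becomes 27.2% with three removed and 24.9% with six; with equal prognosis nothing changes. These figures rest on assumed values of k and of the landmark rates. OS12 is the clearest case. PFS3 and PFS6 move mainly through early deaths and documented early PD.

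Two stronger conclusions are tempting and do not follow. It is not established that the reported rates will be biased upward, because that depends on how many patients are removed and how they fare. And the two-stage decision is not affected by this point: it uses ORR alone, and its stated properties reproduce.

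**What to change.** In SAP section 7.3, add wording such as: *PFS (including PFS3 and PFS6) and OS (including OS12) will be analysed primarily in all treated patients, from the first infusion. The analysis in the efficacy population is supportive.* Make Tables 11.2.2.4 and 11.2.2.5 and the matching figures the main outputs, and label Tables 11.2.2.2 and 11.2.2.3 supportive. For the supportive tables, state whether early-progression patients are included, since section 4.1.1 mentions them only for ORR.

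The ORR analysis set and the two-stage rule stay as they are. The cost is a short SAP edit and relabelling of planned outputs, with no new data, patients or tables. The downside is that headline PFS and OS rates may be slightly less favourable. For PFS the remedy is partial: patients who leave without a scan are still censored at baseline, and that censoring may be informative.
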